3.4.5 Follow-Up Visits

3.4.5.1 Scheduled Visits

Study data will be collected at 1-2 week, 6 weeks, 3 months, 6 months, 9 months, 12 months, and every 6 months thereafter for a total of five years. Subjects will be weighed and given a physical examination. Parents and subjects will meet with the nutritionist at these same visits.

The subjects will maintain the behavior modification program worked out with the nutritionist and psychologist before surgery. These programs are individualized to each subject's dietary habits, eating habits, and quality of life issues. The subject will be encouraged and counseled to combine their Lap-Band tool with long-term modifications in their lifestyle, including exercise. Weight loss, status of pre-operative comorbidities and development of complications will be reviewed at every follow-up visit. This will include testing to follow pre-operative comorbidities. Baseline laboratory and nutritional parameters will be repeated every 3 months for the first year post op. OGTT will be performed at 1 year and 5 year on the subjects who have impaired glucose tolerance at baseline testing (excluding subjects who have type I or II diabetes who is not clinically safe to perform the test). However, if the HbA1c or fasting blood glucose tests show abnormal results or the subject develops polyuria or polydipsia, additional interval testing should be performed based on ADA guidelines.

All laboratory, gastrointestinal, EKG, nutritional, and psychiatric evaluations which were performed at baseline will be repeated every 12 months.

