3.7.6 Statistical Methods

Change in the primary efficacy endpoint, % EWL, will be evaluated by a linear modeling in which the covariance among repeated measures of weight loss from month 6 to month 60 is

modeled. SAS PROC MIXED will be used in which two covariance structures will be examined by means of a REPEATED statement: unstructured (UN) and autoregressive (AR(1)). AIC will be examined to determine the most suitable structure. In the case that AR(1) is selected, a RANDOM statement for Subject will be included in the model. The predictive variable of greatest interest in the model is time. % EWL is expected to increase after surgery, more quickly initially, and then more slowly. To test for this decelerating trend, Time will be log transformed. The residuals of the model will be examined, especially those relative to predicted weight loss over time to ensure that the model is not over or under predicting over the course of follow-up. Systematic departures of the residuals from the predicted time course may require adding a quadratic trend to the model or the choice of a different transformation for time. Covariates used in the model will include baseline weight (as measured by BMI).

The null hypothesis is that % EWL will remain unchanged (i.e., at zero) post surgery. The alternate hypothesis is that % EWL will be positive post surgery. An alpha of 0.05 will be used to determine if the null hypothesis is rejected. The form of the weight loss over time is not part of the hypothesis of the study, but instead is included to better understand the expected trend weight loss follows.

The secondary efficacy endpoint, BMI, will be tested using a model similar to that used to test % EWL. The covariance structure selected for the modeling of % EWL will be applied in the modeling of BMI. Similarly, the same transformation of time will be applied to this endpoint. Baseline BMI will not be included as a baseline covariate, but instead will be assigned a value of time 0 and will be included as an endpoint measure. The null hypothesis is that BMI will show no change from time of surgery. The alternate hypothesis is that BMI will decrease after surgery.

The secondary efficacy endpoint of change in co-morbidities will be examined by McNemar tests. The null hypothesis is that there is no change in each co-morbidity post surgery. The alternate hypothesis is that there will be a change in each co-morbidity.

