3.7.7 Data Collection

Data will be collected by the principal investigator, the nurse practitioner, or nutritionist and documented on a standardized data form. The data will be entered by a research coordinator or the principal investigator in a fashion that maintains patient anonymity, using a unique identification number. The data will be entered into a secure computerized database, which can be accessed only by the principal investigator and the research coordinator with the use of a password. Data collection and statistical analysis will be performed by assigned research personnel, who will access the data using the unique patient identification number assigned.

We will collect relevant life history information from the subject's medical records including illnesses and hospitalizations that occur while subjects are participating in the research, as well as age, ethnic background, marital status, medical history, weight loss, changes in weight-related medical conditions, and information about the surgery and information about lap-band adjustments, and complications. We will collect medical information from physicians and other healthcare providers in General Surgery, Pediatric Surgery, Pediatrics, Psychiatry, and Psychology and from the NYU hospital medical records.

All data will be recorded on case report forms and compared at 6, 12, 24, 36, 48, and 60 months with baseline. Results will be reported descriptively as well as by modeling weight loss in order to assess aggregate outcomes and address the issues of safety and efficacy.

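### The secondary BMI model puts baseline at time 0 but uses log time with no offset, so as written the baseline records drop out and change from surgery is not tested

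*Combined protocol and SAP*

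**What the plan says.** All the modelling text is in section 3.7.6 (Statistical Methods). The primary %EWL model covers months 6 to 60 and expects that "EWL is expected to increase after surgery, more quickly initially, and then more slowly". For that reason, "To test for this decelerating trend, Time will be log transformed". A residual check on that model may lead to a quadratic term or another transformation.

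The secondary endpoint BMI "will be tested using a model similar to that used to test % EWL". Two instructions follow: "Similarly, the same transformation of time will be applied to this endpoint", and "Baseline BMI will not be included as a baseline covariate, but instead will be assigned a value of time 0", with baseline entering as one of the outcome measurements. The hypothesis is explicit: "The null hypothesis is that BMI will show no change from time of surgery". The alternative is a decrease.

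Two other sections bear on this. Section 3.4.5.1 sets the visits: "Study data will be collected at 1-2 week, 6 weeks, 3 months, 6 months, 9 months, 12 months, and every 6 months thereafter", up to five years. Section 3.7.7 adds: "All data will be recorded on case report forms and compared at 6, 12, 24, 36, 48, and 60 months with baseline".

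**The concern.** The two BMI instructions cannot both be carried out. In the %EWL model the first time point is month 6, so the log always exists. The BMI model inherits the log and also receives a record at time 0, where it does not.

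Three things are at stake.

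- **The hypothesis.** The null refers to the time of surgery. If the baseline records fall out, and baseline is by instruction not a covariate, the model contains no pre-operative BMI and its slope cannot address that null.
- **Pre-specification.** If the analyst repairs the model, the offset, the unit and the visits are chosen after data are seen. The months 6 to 60 window is stated only for %EWL. A similar model for BMI could start there or could include the visits at 1-2 weeks, 6 weeks and 3 months.
- **Detection.** The residual check is described for %EWL, which has no time-0 record, so it would not expose the fault.

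**Working it through.** The plan gives no numerical figure for the BMI model, so there is nothing to reproduce. The first step needs no assumptions. The others use assumed BMI courses to show size.

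**1. Records lost.** ln(0) is minus infinity. SAS returns a missing value, and PROC MIXED does not use a record whose covariate is missing. One baseline record per subject is lost, up to 120 (section 3.1). With 120 subjects, baseline and 10 six-monthly visits, 120 × 11 = 1,320 records become 1,200.

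**2. Assumed courses (not from the documents).** BMI is 48 at surgery and falls linearly to month 6. After that:

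- (a) plateau: flat at 38; true change at month 60 is 38 - 48 = -10
- (b) regain: linear from 38 to 41; true change 41 - 48 = -7
- (c) continuing, slowing decline: 42 - 4·ln(t/6)/ln(10), reaching 38; true change -10

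Only (c) follows the pattern that section 3.7.6 expects.

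**3. Literal model.** Equal-weight least squares of mean BMI on ln(months), with t = 0 excluded. The visit sets are 11 visits (6, 9, 12, 18, then six-monthly to 60), 12 visits (month 3 added) and 14 visits (0.35, 1.4 and 3 months added).

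| Slope on ln(months) | (a) | (b) | (c) |
|---|---|---|---|
| 11 visits, months 6-60 | 0 | +1.291 | -1.737 |
| 12 visits | -0.964 | +0.069 | -2.083 |
| 14 visits | -1.896 | -1.318 | -2.055 |

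Fitted change from month 6 to month 60 on the 11 visits is slope × ln(60/6) = slope × 2.303:

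- (a) 0
- (b) 1.291 × 2.303 = +2.97
- (c) -1.737 × 2.303 = -4.00

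In (c) the fit is accurate for its window, but it omits the fall of 6 before month 6. With all early visits the sign is right in all three courses, but baseline is still absent.

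**4. Patched model.** Baseline 48 is kept at t = 0 and BMI is regressed on ln(t + 1). The month-60 change is slope × ln(t60 + 1), with t60 being month 60 in the chosen unit. Days use 30.4375 per month.

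| Month-60 change (days / months / years) | 11 visits + baseline | 14 visits + baseline | True |
|---|---|---|---|
| (a) | -9.89 / -8.16 / -5.44 | -12.39 / -10.18 / -8.14 | -10 |
| (b) | -7.28 / -5.04 / -2.22 | -9.59 / -7.40 / -5.26 | -7 |
| (c) | -10.04 / -9.57 / -7.80 | -12.02 / -10.54 / -9.28 | -10 |

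Every patched estimate is a decrease; only the size moves. Adding a squared ln(t + 1) term for (b) does not remove the dependence: -7.20 / -6.56 / -3.80 on 11 visits and -10.29 / -8.42 / -4.59 on 14.

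**5. Categorical visit.** Month 60 minus baseline returns -10, -7 and -10 directly.

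**6. Effect on the test.** A separate simulation used a random-intercept model with 120 subjects, six-monthly visits and 40 replicates per course. Between-subject SD 6 and residual SD 2 are assumptions. Its courses differ slightly from those above.

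| Assumed course | Literal slope | Literal fit declares a decrease | With an offset |
|---|---|---|---|
| Falls 8 by month 6, then flat | -0.007 | 3% | 100% |
| Falls 10, then regains to -5 | +2.18 | 0% | 100% |
| Steady log decline, true -10.3 | -2.37 | 100% | 100% |

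The last column held for each of four versions: ln(days + 1), ln(months + 1), ln(years + 1) and ln(months + 0.1).

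**The case against.** The strongest reply is that the plan's intent is clear. Baseline is to be kept as an outcome and change from surgery is to be tested, so dropping the baseline records would itself depart from the plan. A competent programmer would see the undefined log and add an offset. Months is the natural unit, since section 3.7.6 gives its window in months, and with plain log time the unit does not affect the slope at all. On the course the plan expects, ln(months + 1) gives -9.57 or -10.54 against a true -10, an error of about 5%. The zero and positive slopes require a plateau or regain that the documents do not predict, together with a start at month 6. All four offsets detected the decrease in every simulated replicate. Section 3.7.7 would in any case display a fall from baseline.

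Most of this stands as a limit on the consequences. It does not remove the fault. The instructions conflict, and the plan does not say how to resolve them. Plain log may be replaced after the residual check, but the trigger is the fit of %EWL, not the time-0 record. The comparisons in section 3.7.7 name no BMI test. Once an offset is needed, its value, the unit and the visits all affect the reported BMI change, and none is fixed in advance.

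**Conclusion.** The concern holds. The BMI rule cannot be run as written. A literal fit loses up to 120 baseline records and cannot test the stated null. That conclusion rests on the text alone.

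The size of the consequence rests on assumed courses and equal-weight fits to visit means; other covariance weights would change the figures somewhat. It depends on how the gap is filled:

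- **Literal fit from month 6:** a continuing decline is understated (-4.0 against -10). A plateau or regain would show no decrease or a rise.
- **Literal fit with all early visits:** the sign is right in the courses examined, but baseline is still not tested.
- **Offset added:** the test of a decrease probably survives. The estimate ranges from -2.2 to -9.6 for the regain course and from -7.8 to -12.0 for the continuing decline.

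One secondary endpoint is affected and the primary %EWL model is not. This should be fixed, but it does not threaten the trial's main conclusion.

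**What to change.** In section 3.7.6, state which visits enter the BMI model. Then do one of the following; either is sufficient.

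1. Use visit as a categorical factor with baseline as a level, and test a pre-specified contrast, for example month 60 minus baseline.
2. Keep continuous time, but pre-specify a transformation that is defined at time 0, with its unit and offset. Check its fit on the BMI series including baseline, and name the contrast to be tested.

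The second option stays closer to the planned model. The first does not depend on the assumed shape over time. The cost is a few sentences of wording, and a few more time parameters if visit is categorical. No new data are needed.

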3.0 INVESTIGATIONAL PLAN

3.1 Study Design

This is a prospective, non-randomized, single-center study to be conducted under an FDA-approved Investigational Device Exemption (IDE). One investigational site will enroll and treat up to 120 subjects who meet the criteria for use of the LAP-BAND® System, except that they are adolescents ages 14 to 17. Subjects will be followed for five years.

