3.2.4 Removal of Subjects from the Trial

A study subject or the parent of the study subject may end their participation in the study at any time. If a subject withdraws, the principal investigator will make reasonable effort to determine the reason for the subjects' withdrawal from the study and complete termination procedures as described in section 3.4.7. Telephone calls, registered letters and offers of transportation to the investigational site are considered reasonable effort.

In addition, the principal investigator may discontinue a patient's participation in the study if the patient fails to comply with the follow-up evaluation schedule (i.e., if patient missed 3 or more sequential follow-up visits.)

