3.3 Study Duration

Subjects will be followed for a period of five years post-operatively.

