The secondary efficacy endpoint of quality of life change, as measured by the SF36 scale, will be examined by testing the mean change against the null hypothesis of zero (no change) by means of a paired t-test. The alternate hypothesis is that improvements will be seen between pre and post surgery in SF36 scale scores. A further analysis will examine whether change in SF36 scale scores is correlated with amount of weight lost.

The secondary efficacy endpoint of depression change, as measured by the child depression inventory, child behavior checklist, and youth evaluation scale, will be examined by testing the mean change against the null hypothesis of zero (no change) by means of a paired t-test. The alternate hypothesis is that improvements will be seen between pre and post surgery in depression inventory scores. A further analysis will examine whether change in depression is correlated with amount of weight lost.

Descriptive statistics will be provided for secondary variables such as nutrition status, psychiatric evaluations, etc.

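### The paired t-tests for SF-36 and depression change use complete pairs only, with no visit or missing-data rule named, so loss related to response would bias the estimate in either direction

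*Combined protocol and SAP*

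**What the plan says.** Section 3.7.6 uses the same sentence for SF-36 change and for depression change (CDI, CBCL and YES): each "will be examined by testing the mean change against the null hypothesis of zero (no change) by means of a paired t-test". For SF-36, "The alternate hypothesis is that improvements will be seen between pre and post surgery in SF36 scale scores"; the depression alternative is worded in parallel. Neither paragraph names the post-surgery visit, the analysis set, the handling of missing scores, or whether the test is one- or two-sided. The statement "An alpha of 0.05 will be used to determine if the null hypothesis is rejected" belongs to the primary endpoint.

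The scales are collected repeatedly. Section 3.4.5.1 says that "psychiatric evaluations which were performed at baseline will be repeated every 12 months", and Table I places SF-36, CDI, CBCL and YES at screening and at years 1, 2, 3, 4 and 5. Section 3.7.7 compares all data with baseline at 6, 12, 24, 36, 48 and 60 months.

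Loss is foreseeable. Section 3.3 says "Subjects will be followed for a period of five years post-operatively". Section 3.2.4 says "A study subject or the parent of the study subject may end their participation in the study at any time" and lets the investigator discontinue a subject who misses three or more visits in a row.

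The same statistical section treats weight differently. %EWL and BMI are analysed in PROC MIXED with the repeated measures modelled, and for BMI "Baseline BMI will not be included as a baseline covariate, but instead will be assigned a value of time 0", so baseline enters as a response.

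**The concern.** A paired t-test needs both members of the pair. With no imputation or other rule in the available text, a subject without the later score contributes nothing to that test, even if several earlier post-operative scores are on file. The mean change then describes those who stayed. It equals the mean for everyone treated only if stayers and leavers changed alike.

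Quality of life is named in the secondary objective (section 2.2), and both endpoints are tested for improvement. The study has one arm, so no control group suffers similar loss that could offset the bias: the mean change itself is the efficacy statement. Section 3.7.6 already uses a method that retains incomplete subjects for weight, and gives no reason for using a weaker one here.

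**Working it through.** The plan has no figure to reproduce. It states no power, SD, effect size or retention for these endpoints, and no derivation of the 120.

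**Inputs.** From the documents: N = 120 (section 3.1: "One investigational site will enroll and treat up to 120 subjects") and alpha 0.05, borrowed from the primary endpoint and taken as two-sided. Assumed: the proportion lost d, the gap g between the mean change of completers and of those lost (in SD of change), and the simulation settings in step 3.

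**Step 1: bias of the completer mean.** The all-subject mean is (1 − d) × (completer mean) + d × (mean of those lost). Hence

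bias = completer mean − all-subject mean = d × g.

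**Step 2: effect on the test.** If the true all-subject change is zero, the paired t-test on n = 120 × (1 − d) subjects has noncentrality d × g × √n (SD of change among completers set to 1). For d = 0.40 and g = 0.5: n = 72, noncentrality = 0.20 × √72 = 1.70, critical value 1.99, rejection rate 38.8%.

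| Lost d | n | Bias in SD at g = 0.25 / 0.5 / 1.0 | Rejection rate under a true zero change |
|---|---|---|---|
| 10% | 108 | 0.025 / 0.05 / 0.10 | 5.8% / 8.1% / 17.8% |
| 20% | 96 | 0.05 / 0.10 / 0.20 | 7.7% / 16.3% / 49.2% |
| 40% | 72 | 0.10 / 0.20 / 0.40 | 13.3% / 38.8% / 91.7% |

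At g = 0 the bias is zero and the rejection rate 5% for any d. A negative g reverses the sign: d = 40% and g = −0.5 give −0.20 SD.

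**Step 3: does using the earlier scores help?** Simulation with 120 subjects, year-1 and year-5 change correlated 0.6, true year-5 change 0.30 SD, and about 40% to 42% missing at year 5. The log-odds of loss move by 1 per SD of the driving score. The all-visit estimate regresses year 5 on year 1 among completers and averages the prediction over all 120.

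| Loss depends on | Completer mean | All-visit estimate |
|---|---|---|
| nothing (random) | 0.30 | 0.30 |
| poor year-1 change | 0.51 | 0.30 |
| good year-1 change | 0.09 | 0.30 |
| poor, unseen year-5 change | 0.65 | 0.54 |

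The second row agrees with step 1: the bias is 0.51 − 0.30 = 0.21, the loss is 1 − 0.583 = 0.417, and 0.21 / 0.417 gives a gap of 0.50 SD.

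**Step 4: precision when loss is random.** In large samples the ratio of standard errors is √(1 − 0.6² × 0.40) = √0.856 = 0.925, so the all-visit estimate is about 7% to 8% more precise.

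**Step 5: instrument ages.** Section 3.4.2 gives the CBCL a target age of 6 to 18 and the YES 12 to 20. Subjects enter at 14 to 17, so at year 5 they are 14 + 5 = 19 to 17 + 5 = 22. All are then past the CBCL range, and those who entered at 16 or 17 are past the YES range (21 or 22). The first to leave are those who entered at 17: at year 2 for the CBCL (19) and year 4 for the YES (21).

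**The case against.** A reader might infer that later-year improvement will be overstated, because adolescents who do badly stop attending. The documents do not support that as fact. They report no retention and do not say who leaves. Section 3.7.6 treats the link between score change and weight lost as something still to be examined. The simulation shows the opposite bias just as readily.

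Nor do the documents say that the tests are run on whoever attends a late visit. They speak only of before and after surgery. If month 12 were the tested visit, there would be less time for loss and probably less bias. Section 3.7.7 also means that earlier visits are reported, although they would not inform the later estimate.

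Three further points stand. A mixed model does not cure loss that depends on unseen scores: 0.54 against a true 0.30 is better than 0.65 but still wrong. The BMI analysis cannot be copied as it is, because it uses transformed continuous time and a covariance structure chosen for %EWL. Late CBCL and YES scores may be missing or off-norm because of age, which no choice of model repairs.

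None of this rescues the paired t-test. Uncertainty about direction favours a method that is right in both directions when loss depends on observed scores, and no scenario run here made the all-visit estimate materially more biased.

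**Conclusion.** The point holds as a conditional one. As written, both tests rest on complete pairs, discard annual scores that the study collects, and leave the visit and missing-data handling open. The estimate is unbiased if loss is unrelated to response, too high if poor responders leave and too low if good responders leave.

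The size cannot be known from the documents. With about 40% lost and gaps of 0.25 to 0.5 SD between completers and those lost, the completer mean is off by 0.1 to 0.2 SD, and by more if the gap is wider. With 10% lost and gaps of 0.25 to 1 SD, it is off by about 0.03 to 0.10 SD. Everything except N = 120 and alpha is an assumption.

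The change should be made: the endpoints are secondary and the primary %EWL analysis is untouched, but the weakness is avoidable.

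**What to change.** In section 3.7.6, replace both paired t-tests with a repeated-measures mixed model for each scale:

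- PROC MIXED with baseline and all annual scores as responses, visit as a categorical factor, unstructured covariance (6 occasions, 6 × 7 / 2 = 21 parameters) and Kenward-Roger degrees of freedom.
- Name the visit, and test the change-from-baseline contrast there. State whether the test is one- or two-sided.
- Describe the model in its own right. It shares with the BMI analysis the use of baseline as a response, but not the transformed continuous time.
- Report the number observed at each visit, and keep the paired t-test as a supportive analysis.
- Add a sensitivity analysis for loss that depends on unseen scores, for example by shifting the assumed later scores of those lost over a stated range.
- For the CBCL and YES, restrict the modelled visits to the instruments' stated age ranges, or flag scores outside them.

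The cost is SAP wording and programming, with no new data. With complete data the contrast reproduces the paired mean change, so nothing is given up. With incomplete data, the reported improvement may become smaller.
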